8.1.3. Listings of Serious Adverse Events (SAE), Adverse Event Dropouts, and Death

SAE data will be reported as related and not related. The two categories will be defined as follows:

- Related combines the options definitely, probably, and possibly
- Not related is not related.

Participant data listing for SAEs will be by cohort, and arm, sorted by reported date within participant. Unique information included on the first page of the listing contains SAE onset and resolution dates and times; verbatim description of SAE; severity and relationship to study medication, action taken, and outcome.

A tabulation will present participants who discontinue study drug prematurely for the doxycycline PEP arm due to an adverse event, and the reasons for discontinuations:

- Requirement for prohibited concomitant medications or other contraindication to doxycycline.
- Occurrence of an adverse event requiring discontinuation of doxycycline.
- Request by participant to terminate study treatment.
- Clinical reasons believed life threatening by the physician, even if not addressed in the toxicity section of the protocol.
- Requirement for chronic tetracycline use (>14 days).

8.2. Laboratory Data

Laboratory data collected in this study consist of hematologic and liver function tests at months 3 and 9 in those on doxycycline PEP arm:

- Complete blood count (CBC) (white count, hemoglobin, platelets).
- Liver function testing (AST, ALT, total bilirubin and alkaline phosphatase)

The presentation of laboratory results focuses on the change from baseline to 3 and 9 months. All participants in the doxycycline PEP arm who have a baseline and at least one follow-up laboratory assessment, unless permanently discontinued doxycycline PEP, will be included in the presentation of the laboratory data. For each laboratory test, descriptive statistics will summarize the results at baseline, 3-, and 9-month assessment, and the change from baseline to 3- and 9-months assessments. The summary statistics are N, mean, s.d., median, and range. The within-group p-value from the paired t-test on the mean change from baseline and the 95% confidence interval limits for the mean change from baseline are also included with the change descriptive statistics. Figures will also be used to display change from baseline to 3 and 9 months.

The quantitative laboratory data for participants who have a baseline and follow-up laboratory assessment may be presented as scattergrams plotting the change from baseline as a function of the baseline value.

This analysis will omit values occurring after a participant has permanently discontinued study drug.

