1.2.1 Doxycycline Safety

Several features of doxycycline make it an optimal choice for STI PEP. Doxycycline has been used safely and for extended durations as prophylaxis against infections such as malaria²³ and for non-infectious conditions including rosacea²⁴ and acne vulgaris.²⁵ Doxycycline is generally safe and well-tolerated when used chronically. Side effects include mild gastrointestinal symptoms, photosensitivity, and rarely pill esophagitis and pseudotumor cerebri.²⁶ Reassuringly, doxycycline has a much lower risk than other antibiotics for the antibiotic-associated diarrhea caused by C. difficile infection,^{27, 28} and may even exert a protective effect against C. difficile.^{29, 30} Doxycycline is a scalable PEP intervention, as it is generic, inexpensive, and widely available. Doxycycline does not require dose adjustment in hepatic or renal failure, including dialysis. In the IPERGAY doxycycline PEP study, there was no difference in grade 3 or 4 adverse events between the study arms. As anticipated, there were more gastrointestinal side effects in those on PEP (25%) vs. the non-PEP control arm (14%). Discontinuation of doxycycline was uncommon with 8 study participants (7%) stopping doxycycyline due to side effects attributed to doxycycline, the majority of which were gastrointestinal.¹ Given the safety profile of doxycycline and the enrollment of participants receiving ongoing clinical care for HIV or HIV PrEP, study-specific monitoring will be limited to complete blood count and liver function tests at months 3 and 9 to assess for hematologic and hepatic toxicity, which occur rarely with chronic doxycycline use (<1%). Assessment for side effects (eq., pill esophagitis. photosensitivity, new onset headaches), with clinical and laboratory testing if indicated if potential serious adverse events are suspected. Participants will receive standard of care monitoring through their HIV or PrEP. Typical standard of care monitoring for PLHIV includes semi-annual viral load monitoring, renal and liver function tests, and annual CBC. Typical standard of care monitoring for PrEP patients includes guarterly HIV tests and semi-annual or annual renal monitoring.

1.2.2 Rationale for single dose doxycycline as STI PEP.

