6.2 Study visits

Specific study procedures are detailed in Table 6.1. Visits will take place at enrollment and quarterly thereafter, up to 12 months. Interim visits may be scheduled for diagnosis and treatment of STI and collection of additional specimens or for evaluation of possible doxycycline associated adverse events. Participants may also request interim STI testing.

6.2.1 Enrollment Visit After confirming eligibility through pre-screening and prior to study procedures, we will obtain written informed consent and collect locating information; the latter will be updated at each study visit. At enrollment, demographic, behavioral, and clinical information will be collected and a release of information obtained to permit access to medical records. STI testing for chlamydia and gonorrhea through nucleic acid amplification testing (NAAT) of clinician or self-collected pharyngeal and rectal swabs and first void urine will be conducted. Serologic testing for syphilis will be conducted. If required STI testing has been conducted within past 30 days, these results may be used for the enrollment evaluation. Participants diagnosed with an STI at baseline will be treated; presence of a baseline STI will not preclude enrollment but STI's present at time of enrollment will not count towards study endpoints. All STIs will be reported to the local health department as required per local standard procedures.

Randomization Within 14 days of enrollment, participants will be randomized in a 2:1 ratio to openlabel doxycycline PEP or the standard of care control condition (regular STI counseling, screening and treatment as indicated). The randomization code and resulting allocation list will be generated and maintained by the study statistician. The list will be blocked and stratified by site. While neither participants nor study staff will be blind to each participant's randomization group once assigned, the randomization scheme will utilize varying block sizes in order to protect the blind prior to randomization of each participant.

- 6.2.2 Quarterly visits after enrollment. Quarterly visits will be conducted every 90 days, +2 weeks/ -10 weeks. Participants unable to attend a quarterly visit will be asked to return for an unscheduled visit as soon as feasible. The quarterly evaluations should be completed at the time of this visit. Subsequent visits should occur on the assigned quarterly scheduled to the extent possible.

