6.3.20 ART and PrEP status

For PLWH, current ART regimen and status (taking vs. not taking) will be recorded at each visit. At entry and month 12 for PLWH, the most recent HIV RNA and CD4⁺ cell count available from clinical visits will be recorded if available

For participants on PrEP At each visit for those on PrEP, PrEP status will be assessed (taking vs. not taking, and how PrEP is taken- daily vs intermittent). At entry and month 12, the most recent HIV antibody or viral load test results from clinical care will be recorded.

6.3.21 **Hematologic and liver function tests**: Complete blood count (CBC) (white count with differential, hemoglobin, platelets) and liver function testing (AST, ALT, total bilirubin and alkaline phosphatase)

will be drawn at months 3 and 9 in those on doxycycline PEP. Testing done through standard of care within 30 days of the study visit may also be used if available. For those in the standard of care arm, CBC will be done at the month 12 visit. In the event that a CBC cannot be obtained at month 12, an available CBC from any time during study participation may be used.

- 6.3.22 **Serum for storage** (Optional): At months 0 and 12, 10 mL of serum will be collected for storage for future analysis (non-genetic) in participants who agreed to this. Serum may be collected up to 14 days after the visit if blood cannot be collected at the time of the visit.
- 6.3.23 **Reimbursement**: Participants will be reimbursed at the enrollment visit, at quarterly visits, and at the time of return for treatment of STIs with accompanying collection of swabs. An additional reimbursement will be provided for participants who consent to the optional stool sample collection at the baseline, 6 month, and 12 month timepoints. No reimbursement will be provided at other unscheduled interim visits such as visits to provide additional doxycycline.

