6.5.1. Baseline Laboratory Data

Baseline bacterial STI diagnoses (GC/CT, Syphilis) detected by lab-based study testing will be reported for each cohort separately, by arm and by study site. Infections will be tabulated by sites(s) of infections

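### SAP 8.2 rests the laboratory safety presentation on a baseline blood count and liver panel that no running text schedules or sources; separately, the SAP holds two recording rules for grade 2+ laboratory abnormalities

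*SAP*

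**What the plan says.** **Laboratory presentation.** SAP 8.2 opens with "Laboratory data collected in this study consist of hematologic and liver function tests at months 3 and 9 in those on doxycycline PEP arm". It continues: "The presentation of laboratory results focuses on the change from baseline to 3 and 9 months". Inclusion is limited to "All participants in the doxycycline PEP arm who have a baseline and at least one follow-up laboratory assessment", setting aside those who have permanently stopped doxycycline. The section then plans summaries at baseline and follow-up, mean changes with paired t-tests and 95% confidence intervals, figures, and optional plots of change against baseline.

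The rest of the running text gives the same two time points. Protocol 1.2.1 states that "study-specific monitoring will be limited to complete blood count and liver function tests at months 3 and 9". Protocol 6.3.21 states that the tests "will be drawn at months 3 and 9 in those on doxycycline PEP". The enrollment visit in Protocol 6.2.1 names STI tests only, and its allowance for earlier results is confined to those: "If required STI testing has been conducted within past 30 days, these results may be used for the enrollment evaluation". SAP 6.5.1 is titled Baseline Laboratory Data, but its content is "Baseline bacterial STI diagnoses (GC/CT, Syphilis) detected by lab-based study testing will be reported", with no CBC or LFT.

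**Recording of grade 2+ hematologic and hepatic abnormalities.**
- SAP 3.5 and Protocol 7.1 take only those that the site investigator attributes to doxycycline. Both also take every SAE, with no attribution condition.
- SAP 2.2.2.2 and SAP 8.1.1 take all such abnormalities. In SAP 8.1.1 the attribution condition is attached to the grade 3 and 4 AEs, not to the laboratory item.
- SAP 8.1.2 tabulates these events by grade and arm and, in the doxycycline arm, by relatedness. SAP 8.1.3 defines the relatedness categories, one of which is not related.
- SAP 3.5 and Protocol 7.2 call for attribution to be recorded in those randomized to doxycycline.

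**The concern.** The two parts of SAP 8.2 do not fit together. The section describes a data collection without a baseline, then makes a baseline value the condition of entry and the reference for every planned comparison. An analyst following it would either have no pairs or would have to choose chart values by a rule written after the data exist. The entry condition would also keep out of this section month 3 and 9 results that the study did collect, for every participant without a chart baseline.

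The recording rule raises a separate problem in SAP 8.1.2. If sites followed the attributed-only rule, a near-empty control column or a near-empty not-related row would come largely from that rule. If they recorded everything, the same pattern would carry safety information. The reader of the table cannot tell which applies. This matters because Protocol 1.2.8 already summarizes safety in terms of doxycycline-associated events.

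**Working it through.** **1. Is a baseline scheduled or sourced?** Four places could supply one: Protocol 1.2.1, 6.2.1 and 6.3.21, and SAP 6.5.1. None names a baseline CBC or LFT. There are two 30-day allowances for care results. The one in Protocol 6.2.1 concerns STI tests. The one in Protocol 6.3.21 directly follows the month 3 and 9 draws and does not mention enrollment. The schedule of events is damaged in the copy reviewed, so it is not used. Scheduled baseline draws found: 0.

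**2. How many analyses depend on it?** SAP 8.2 lists white count, hemoglobin and platelets (3), and AST, ALT, total bilirubin and alkaline phosphatase (4).
- Analytes: 3 + 4 = 7
- Paired change analyses: 7 × 2 follow-up times = 14
- Scheduled pairs in each: 0

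**3. How many collected values could the entry rule exclude?** With 2:1 allocation and two scheduled draws per doxycycline-arm participant:

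| Enrolled | Doxycycline arm | Scheduled participant-visits |
|---|---|---|
| 780 (planned) | 780 × 2/3 = 520 | 520 × 2 = 1,040 |
| 554 (at interim review, Protocol 1.2.8) | 554 × 2/3 ≈ 369 | 369 × 2 = 738 |

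These are upper bounds. They assume full attendance, no permanent discontinuation, and no participant with a usable care baseline.

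**4. Where might a care baseline exist?** Protocol 1.2.1 says of HIV care: "Typical standard of care monitoring for PLHIV includes semi-annual viral load monitoring, renal and liver function tests, and annual CBC". For PrEP care it names HIV tests and renal monitoring, with no CBC or LFT. Chart baselines would therefore probably be commoner in the HIV cohort. The documents give no figure for either cohort.

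**5. What does each recording rule let into SAP 8.1.2?** For a grade 2+ laboratory abnormality:

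| Event | Attributed-only rule (SAP 3.5, Protocol 7.1) | Unfiltered rule (SAP 2.2.2.2, 8.1.1) |
|---|---|---|
| Doxycycline arm, attributed | recorded | recorded |
| Doxycycline arm, unattributed, not serious | missing | recorded |
| Doxycycline arm, unattributed, meets SAE definition | recorded as SAE | recorded |
| Control arm before roll-over, not serious | missing | recorded |
| Control arm before roll-over, meets SAE definition | recorded as SAE | recorded |

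The rules differ only for unattributed, non-serious events, and they do so in both arms.

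**6. Are the arms tested alike?** No. Under Protocol 6.3.21 the doxycycline arm has CBC and LFT at months 3 and 9. The control arm has one CBC at month 12, or another available CBC if that is missed; the text names no control-arm LFT. Fewer control events would be expected under either rule.

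**The case against.** **Care records can supply the baseline.** SAP 8.2 admits those who have a baseline and does not assume that everyone does. Participants are in ongoing HIV or PrEP care, and Protocol 6.2.1 obtains a release for medical records. This stands in part. A reader might infer that the change analysis must be empty and that all 1,040 visits are lost. The documents do not support that: they show zero scheduled pairs, not zero obtainable ones. What remains is that neither source nor window is defined.

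**The versions differ.** The SAP is version 1.0, based on Protocol 5.0, and the protocol supplied is 9.0. An earlier baseline draw cannot be excluded, so the first part rests mainly on SAP 8.2 itself, whose account of the data collected contains no baseline.

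**Unrelated events can still appear.** A reader might infer that the attributed-only rule forces the not-related row and the control column to zero. It does not, because SAP 3.5 and Protocol 7.1 also take every SAE. A serious laboratory abnormality would be recorded even if judged unrelated or if it arose in a control participant. Only the non-serious ones are missing.

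**The consequence is modest.** No between-arm AE tests are planned (SAP 8). Mean laboratory change is not a named safety endpoint in SAP 2.2.2.2 or Protocol 10.1.2, and the grade 2+ table needs no baseline. All of this is correct and limits the weight of the point.

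**Conclusion.** Both parts hold, as separate inconsistencies with separate remedies.

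SAP 8.2 contradicts itself on the baseline. Fourteen change analyses have no scheduled pairs, and their actual size depends on undefined care records that are probably uneven by cohort. Between none and 1,040 scheduled participant-visits (about 738 at 554 enrolled) would be excluded, depending on how many doxycycline-arm participants have a usable record. That the text is inconsistent is firm; the number of values lost cannot be determined from the documents.

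The recording rules conflict within the SAP, and one of them conflicts with the protocol. The choice decides whether unattributed, non-serious abnormalities appear in SAP 8.1.2.

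A reader might infer that settling the rule would make that table a fair comparison of arms. It would not, because the arms are tested at different times and with different panels. Nor does the point reach further into the trial: primary efficacy, SAE and discontinuation reporting do not depend on it. It should be corrected, but it does not threaten the main conclusions.

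**What to change.** **SAP 8.2.** Drop the baseline requirement. Present values and DAIDS grades at months 3 and 9 for all doxycycline-arm participants tested, and keep the existing rule on values after permanent discontinuation. Grading the collected values also gives a doxycycline-arm count that does not depend on the recording rule. Keep change from baseline only as a supportive analysis, in those with a pre-randomization care result within a stated window, and give N by cohort.

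**Recording rule.** Reconcile Protocol 7.1 and SAP 3.5 with SAP 2.2.2.2, 8.1.1 and 8.1.2 into one rule, and state which rule sites actually applied. If it was the attributed-only rule, limit the SAP 8.1.2 laboratory table to the doxycycline arm, which SAP 8 already allows, and label it as attributed events plus any that meet the SAE definition. In any by-arm table, show the number tested per arm and per test.

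**Cost.** Wording changes, which SAP 1 permits before database lock, plus optional chart abstraction under the existing records release. No new procedure is needed. The supportive change analysis may be small and uneven by cohort. If unattributed, non-serious abnormalities were not recorded, they cannot be compared between arms, and the report should say so.

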8 CLINICAL MANAGEMENT ISSUES

8.1 Toxicity

Only toxicities related to study medications provided through the study will be considered in the toxicity management section.

Grade 1 or 2

Participants who develop Grade 1 or 2 toxicity (per DAIDS toxicity table) felt to be related to doxycycyline may continue study treatment at the discretion of the site investigator with close followup. If a participant chooses to discontinue study treatment, the site should notify the study protocol team within 7 days. These participants will remain on study, off study treatment and have all evaluations performed per the SOE.

Grade 3

- Participants who develop a Grade 3 toxicity thought by the site investigator to be related to study
 drug should have doxycycline PEP withheld and the site should consult with the core protocol
 team. The participant should be reevaluated weekly until the AE returns to Grade ≤2, at which
 time study drug may be reintroduced at the discretion of the site investigator in consultation with
 the protocol team.
- Participants experiencing Grade 3 toxicity requiring permanent discontinuation of doxycycline PEP should be followed weekly until resolution of the toxicity. Participants will have premature study treatment discontinuation evaluations performed as noted on the SOE. These participants will remain on study, off study treatment and have all evaluations performed per the SOE.

Grade 4

- Participants with Grade 4 asymptomatic laboratory abnormalities may continue doxycycline PEP if the site investigator has compelling evidence that the toxicity is NOT related to study drug.
- Participants who develop a Grade 4 symptomatic toxicity will have doxycycline PEP permanently discontinued and the site should notify study team within 72 hours.
- Participants experiencing Grade 4 toxicity requiring permanent discontinuation of doxycycline PEP should be followed weekly until resolution of the AE or return to baseline. These participants will remain on study, off study treatment and have all evaluations performed per the SOE.

•

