9 CRITERIA FOR DISCONTINUATION

9.1 Premature Study Treatment Discontinuation

- Requirement for prohibited concomitant medications or other contraindication to doxycycline
- Occurrence of an adverse event requiring discontinuation of doxycycline
- Request by participant to terminate study treatment
- Clinical reasons believed life threatening by the physician, even if not addressed in the toxicity section of the protocol
- Requirement for chronic tetracycline use (>14 days)

Participants who stop doxycycline PEP should be continued on study, off doxycycline PEP with continued evaluations as per the SOE. The reason for doxycycline discontinuation should be recorded.

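### SAP 8.2 gives two conflicting rules for participants who permanently stop doxycycline; read literally, one of them also discards their on-drug laboratory results

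*SAP*

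**What the plan says.** SAP 8.2 defines who enters the laboratory presentation. Doxycycline-arm participants with a baseline value and "at least one follow-up laboratory assessment, unless permanently discontinued doxycycline PEP, will be included in the presentation of the laboratory data". The section ends with a different rule: "This analysis will omit values occurring after a participant has permanently discontinued study drug". The first rule acts on participants and has no time limit. The second acts on individual values.

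Protocol 8.1 links permanent stopping to toxicity: "Participants who develop a Grade 4 symptomatic toxicity will have doxycycline PEP permanently discontinued". It also provides for permanent discontinuation after some Grade 3 toxicity. Protocol 9.1 lists among the reasons for ending treatment: "Occurrence of an adverse event requiring discontinuation of doxycycline". Participant request and a need for prohibited or long-term tetracycline medication are on the same list.

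People who stop are not withdrawn. Protocol 9.1 states: "Participants who stop doxycycline PEP should be continued on study, off doxycycline PEP with continued evaluations as per the SOE". Protocol 8.1 says the same for toxicity stops.

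SAP 5.2.2 defines a Safety Population of everyone who took one or more doses. SAP 8.2 does not use it and gives no reason for the narrower set.

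**The concern.** Protocol 1.2.1 gives the purpose of the month 3 and month 9 blood counts and liver tests as looking for rare hematologic and hepatic toxicity. A rule that removes participants according to whether they later stopped selects on a consequence of treatment. Some of those removed will have stopped because of toxicity, and their on-drug results would go with them. The quantitative display would then describe people who stayed on the drug, while being read as describing the doxycycline arm.

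The conflict is also a practical problem. Two programmers working from SAP 8.2 could build different datasets, and both could claim to have followed the plan.

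**Working it through.** The plan states no figure that could be reproduced here. The check compares the two rules and then gives a scale.

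**The two rules side by side** (a baseline value is assumed available, and the month 3 and month 9 draws done):

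| Time of permanent stop | Participant rule | Value rule |
|---|---|---|
| Before month 3 | nothing shown | nothing shown |
| Between months 3 and 9 | nothing shown | month 3 kept |
| After month 9 | nothing shown | months 3 and 9 kept |
| Temporary interruption, then restart | all kept | all kept |

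If the participant rule holds, the value rule has nothing left to act on. If the value rule is meant, the participant rule is wrong. They differ for people who stop permanently after their first follow-up draw. Someone who stops at month 10 loses two on-drug results under the participant rule and none under the value rule.

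**Do values after stopping exist?** Protocol 8.1 and 9.1 keep these people on the schedule of events, and Table 6.1 schedules the tests for the intervention arm at months 3 and 9. Protocol 6.3.21 ties the draws to people taking PEP, so a site might not draw after a stop. Values from before the stop exist on either reading.

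**What still reports toxicity?** SAP 8.1.2 tabulates Grade 2 or higher hematologic and hepatic events by grade and arm. SAP 8.1.3 lists serious adverse events and tabulates discontinuations due to an adverse event. Neither excludes people who stopped. How complete this is depends on the capture rule. Protocol 7.1 and SAP 3.5 record Grade 2 or higher laboratory abnormalities only when the site investigator attributes them to doxycycline; SAP 8.1.1 has no such limit. Under the narrower rule, a non-serious, unattributed Grade 2 result in someone who stopped could be missing from both the adverse event table and the laboratory presentation. Grade 1 shifts are outside the adverse event table in any case.

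**Scale.** Inputs:
- Planned doxycycline arm: 2 × 260 = 520 (Protocol 10.2).
- Stopping for side effects in the earlier trial: "8 study participants (7%) stopping doxycycyline due to side effects attributed to doxycycline" (Protocol 1.2.1, which adds that most of these side effects were gastrointestinal).
- Hematologic and hepatic toxicity with chronic use: under 1% (Protocol 1.2.1).

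Participants excluded, if the 7% carries over: 0.07 × 520 = 36.4, about 36. At an assumed 3% to 10% the range is 0.03 × 520 = 15.6 (about 16) to 0.10 × 520 = 52. On the 554 enrolled at interim review (Protocol 1.2.8), two thirds is about 369, and 0.07 × 369 = 25.8, about 26. Stops for other reasons would add to these numbers.

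Toxicity at the upper bound: 0.01 × 520 = 5.2, about 5, or 5/520 = 0.96%. With 36 people removed, 520 − 36 = 484 remain. If all 5 are among those who stopped, the presentation shows 0/484 = 0%. If none are, it shows 5/484 = 1.03%. The documents do not say where between these limits the truth would lie.

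**The case against.** The strongest reply is that the closing sentence of SAP 8.2 makes sense only if people who stop contribute values up to that point. The authors may therefore have intended an ordinary on-treatment display and worded the inclusion sentence badly. That may be so, but the inclusion sentence says otherwise, and the plan does not settle which rule governs.

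A reader might infer more than the documents support, in four ways:

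- **That the two rules add up to a double exclusion.** They cannot; they contradict each other.
- **That omitting values after stopping is itself an error.** For an on-drug summary it is a normal choice. Protocol 1.1 gives a half-life of 20 hours, and a scheduled draw may fall weeks or months after the last dose, so pooling such values could dilute an on-drug mean change. The weakness is that they are not shown anywhere in the laboratory presentation.
- **That toxicity cases vanish from safety reporting.** They do not, given SAP 8.1.2 and 8.1.3. A Grade 2 or higher laboratory abnormality that led to stopping and was attributed to doxycycline is captured even under the narrower rule.
- **That the excluded group is several times the expected number of toxicity cases and so probably contains them.** Setting 7% against 1% compares mainly gastrointestinal stops with hematologic and hepatic toxicity. It says nothing about the overlap.

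Two further points stand. Protocol 1.2.8 reports no doxycycline-associated adverse event of Grade 2 or higher at interim review, which suggests that few attributed cases were at stake by then. And SAP 8.2 requires a baseline value although Protocol 6.3.21 schedules none in the doxycycline arm, so the change-from-baseline set may be small whatever happens to the stopping clause. Neither point resolves the conflicting wording.

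**Conclusion.** The concern holds for the quantitative laboratory presentation in SAP 8.2 and goes no further. The section contains two incompatible rules. The literal participant-level rule selects on a treatment outcome, discards on-drug results, and departs without explanation from the SAP's own Safety Population. Its likely direction is toward a cleaner picture than the treated group would give, because some permanent stops are for toxicity. That direction is an inference: stops also occur for unrelated reasons, and the documents give no rate of laboratory toxicity among people who stop.

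The number excluded, about 36 of 520, rests on carrying over the earlier trial's 7%. The size of the resulting bias cannot be derived. The wording should be corrected before the laboratory tables are produced, because the literal reading affects the display meant to monitor these tests and the repair is cheap.

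**What to change.** In SAP 8.2:

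1. Delete the clause that excepts participants who permanently discontinued, and present laboratory data in the Safety Population of SAP 5.2.2. Control participants who rolled over to doxycycline under Protocol 1.2.8 would also meet that definition, so state how they are shown.
2. Limit the closing sentence to the on-drug summary, which keeps every value up to permanent discontinuation.
3. Flag values after permanent discontinuation as off drug and show them in an all-values summary or a listing.
4. List individually the laboratory values of participants who stopped for an adverse event.

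The flag needs only the discontinuation date. Time since last dose should not be required, because dosing is event-driven and the documents name no last-dose date tied to each draw. The attribution difference between Protocol 7.1 with SAP 3.5 and SAP 8.1.1 should be reconciled separately, since it decides how complete the adverse event tables are.

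The cost is a change of wording, one extra flag and one extra table or listing. No further blood draws are needed. The reported summaries may look slightly less favourable.
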